5.2 Handling of Missing Data

5.2.1 Missing Efficacy Endpoints

Missing data will be replaced for the efficacy endpoint in the ITT analyses using the Last observation carried forward (LOCF) method.

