10.4 Statistical Analyses

For continuous variables, descriptive summaries will display number of subjects, arithmetic mean, geometric mean (as appropriate), standard deviation, median, minimum, and maximum by treatment group. For categorical variables, counts and percentages will be displayed.

In general, missing data will not be imputed with the exception that for the ITT analysis, missing viral load results will be imputed using the last-observation-carried-forward (LOCF) methodology.

Additional details regarding statistical methods will be provided in the Statistical Analysis Plan.

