5.1 Methodological Considerations

General Conventions

SAS software (version 9.4 or higher) will be used for all data analyses and tabulations.

The study is not powered for hypothesis testing. P-values will be considered descriptive and will not be adjusted for multiplicity.

Data for all investigational centers will be pooled for analysis.

Unless specified elsewhere, baseline is defined as the last available measurement prior to administration of study drug. Change from baseline will be calculated as the post-baseline value minus the baseline value.

Summary tables will include the data based upon the protocol scheduled time points. For subjects who are early discontinued from the study, all efficacy assessments captured at the ET visit will be assigned to the nearest protocol scheduled time point.

Visit of Treatment Period	Range*	Target Day
Visit 1 / Baseline (Day 1)	Study Day = 1	Day 1
Visit 2 / Day 2	Study Day = 2	Day 2
Visit 3 / Day 3	Study Day = 3	Day 3
Visit 4 / Day 5 (± 1 day)	Study Day 4 to 6	Day 5
Visit 5 / Day 8 (± 1 day)	Study Day 7 to 9	Day 8

*Study day = date of visit - date of first treatment + 1

Descriptive statistics of continuous variables will include n, mean, standard deviation (SD), median, minimum and maximum. Generally, the minimum and maximum values will be presented to the same decimal precision as the raw values, the mean and median values to one more, and the SD, to two more decimal places than the raw values. Summaries for categorical data will include frequencies and percentages. Percentages will be presented to one decimal place.

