5.5 Efficacy Variables and Analyses

All efficacy analyses will be performed for both the ITT and PP populations with results in ITT as primary and PP as supportive.

Viral load (log base 10 copies/mL) and cycle threshold (Ct) data that are continuous in nature but may be reported as “undetermined” or “inconclusive” or “<LOQ”. All virology data will be included in the efficacy analysis except the samples with “Inconclusive” viral load quantitation and the samples with an “Undetermined” RNase P (RP) internal control Ct value.

For analysis-qualified samples, results of “undetermined” and “<LOQ” will be handled as follows for data summary purpose:

- For viral load reported as “Undetermined”, value 1 will be used to calculate descriptive statistics. This will support the need for logarithm transformation.
- For viral load reported as “<LOQ”, value 5×10^1 will be used to calculate descriptive statistics.

In conjunction with above handling of the viral data scenarios, for purposes of this protocol, clearance of viral infection is defined as achievement of: [1] RP Ct ≥ 0 , AND [2] Average N1 Ct ≥ 32 or Average N1 Ct = “Undetermined”.

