5.5.1 Analysis of Primary Efficacy Endpoint

The primary efficacy endpoint is defined as time-weighted average (TWA) change in log10-transformed viral load by RT-qPCR from baseline to Day 8, where TWA will be derived using the trapezoidal rule:

$$\frac{\sum_{i=a}^{b-1} \{0.5 \times (Y_i + Y_{i+1}) \times (t_{i+1} - t_i)\}}{(t_b - t_a)}$$

Y_i is the change from baseline in log10-transformed viral load by RT-qPCR at Visit i , t is the actual study day at the specified timepoint, a is the baseline visit at Day 1, and b is the Day 8 visit.

At the final analysis, each dose of the RD-X19 device will be compared to sham using an Analysis of Covariance (ANCOVA) model with baseline viral load on log10 scale as a covariate and treatment group as an independent variable.

An example of SAS code for the analysis is as follows:

```
proc glm data=datain;
  class trt;
  model aval = trt base /ss3;
  estimate '4x RD-X19 vs Sham' trt 1 0 -1;
  estimate '7x RD-X19 vs Sham' trt 0 1 -1;
  lsmeans trt /pdiff stderr cl;
run;
```

where AVAL denotes the variable to be analyzed, BASE denotes the covariate baseline value, and TRT denotes treatment group with values 1 for 4 Days RD-X19, 2 for 7 Days RD-X19, and 3 for Sham.

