Source: Listing 16.2.4.1, 16.2.9.3

O:\Studies\EmitBio\EB-P12-01\Biometrics\Programs\Tables\xxx.sas ran on Month Day, Year at hh:mm on data from Month Day, Year.

Table 14.2.1.1 – Time-Weighted Average Change in Log10-Transformed Viral Load by RT-qPCR from Baseline to Day 8 for Intent-to-Treat Population

	Statistics	4 Days RD-X19	7 Days RD-X19	Sham
TWA Change in Log10-Transformed Viral Load	N	XX	XX	XX
	Mean \pm SD	XX.X \pm XX.X	XX.X \pm XX.X	XX.X \pm XX.X
	Median	XX.X	XX.X	XX.X
	Min, Max	XX, XX	XX, XX	XX, XX
	LSM (SE)	XX (XX.X)	XX (XX.X)	XX (XX.X)
	95% CI for LSM	(XX.X, XX.X)	(XX.X, XX.X)	(XX.X, XX.X)
RD-X19 vs. Sham				
	LSMD (SE)	XX (XX.X)	XX (XX.X)	
	95% CI for LSMD	(XX.X, XX.X)	(XX.X, XX.X)	
	P-value	0.XXX	0.XXX	

Abbreviation: CI = Confidence Interval; GTM = Geometric Mean; LSM = Least Square Mean; LSMD = Least Square Mean Difference; SE = Standard Error

Note 1: Missing data will be replaced for the efficacy endpoint in the ITT analyses using the Last observation carried forward (LOCF) method.

Note 2: LSM, LSMD, 95% CI for LSMD, and p-values are based on an Analysis of Covariance (ANCOVA) model with baseline viral load on log10 scale as a covariate and treatment group as an independent variable.

Source: Listing 16.2.6.4

O:\Studies\EmitBio\EB-P12-01\Biometrics\Programs\Tables\xxx.sas ran on Month Day, Year at hh:mm on data from Month Day, Year.

Repeat Table 14.2.1.1 for the following:

Table 14.2.1.2 – Time-Weighted Average Change in Log10-Transformed Viral Load by RT-qPCR from Baseline to Day 8 for Per-Protocol Population
 (with Note 1 removed)

Table 14.2.2.1 – Log10-Transformed Viral Load via RT-qPCR by Visit for Intent-to-Treat Population

Study Visit	Statistics	4 Days RD-X19 (N=XX)	7 Days RD-X19 (N=XX)	Sham (N=XX)
Visit 1 /Day 1	N	XX	XX	XX
	Mean ± SD	XX.X ± XX.X	XX.X ± XX.X	XX.X ± XX.X
	Median	XX.X	XX.X	XX.X
	Min, Max	XX, XX	XX, XX	XX, XX
	Geometric Mean on Original Scale	XX.X	XX.X	XX.X
Visit 3 /Day 3	N	XX	XX	XX
	Mean ± SD	XX.X ± XX.X	XX.X ± XX.X	XX.X ± XX.X
	Median	XX.X	XX.X	XX.X
	Min, Max	XX, XX	XX, XX	XX, XX
	Geometric Mean on Original Scale	XX.X	XX.X	XX.X
Visit 4 /Day 5				
Visit 5 /Day 8				

Missing data will be replaced for the efficacy endpoint in the ITT analyses using the Last observation carried forward (LOCF) method.

Note: Geometric Means are computed by exponentiating (base 10) the Means of the log10-transformed viral load.

Source: Listing 16.2.6.4

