Note 1: Clearance of viral infection in saliva is defined as a negative test (Ct value ≥ 32) via RT-qPCR, i.e. achievement of [1] RP Ct =0, AND [2] Average N1 Ct =32 or Average N1 Ct ='Undetermined'. Subjects who did not achieve clearance at the last assessment of the study are considered censored at the time of the last assessment.

Note 2: Subjects who did not achieve clearance at the exit of study are considered censored.

Note 3: Percentiles and 95% CI of median are derived using the Kaplan-Meier method. P-values for treatment comparison are from Log Rank Test.

Source: Listing 16.2.6.4, 16.2.5.3

O:\Studies\EmitBio\EB-P12-01\Biometrics\Programs\Tables\xxx.sas ran on Month Day, Year at hh:mm on data from Month Day, Year.

Figure 15.1.1 - Kaplan-Meier Plot of Time to Clearance of Viral Infection for Intent-to-Treat Population

Figure 15.1.2 - Kaplan-Meier Plot of Time to Clearance of Viral Infection for Per-Protocol Population

Table 14.2.4 – COVID-19 Composite Severity Score by Visit

Population	Study Visit	Category	Statistics	4 Days RD-X19	7 Days RD-X19	Sham
Intent-to-Treat	Visit 1 /Day 1 (Baseline)	Actual Value	N	XX	XX	XX
			Mean \pm SD	XX.X \pm XX.X	XX.X \pm XX.X	XX.X \pm XX.X
			Median	XX.X	XX.X	XX.X
		Actual Value	Min, Max	XX, XX	XX, XX	XX, XX
			N	XX	XX	XX
	Visit 5 /Day 8	Actual Value	Mean \pm SD	XX.X \pm XX.X	XX.X \pm XX.X	XX.X \pm XX.X
			Median	XX.X	XX.X	XX.X
			Min, Max	XX, XX	XX, XX	XX, XX
		Change from Baseline	Mean \pm SD	XX.X \pm XX.X	XX.X \pm XX.X	XX.X \pm XX.X
			Median	XX.X	XX.X	XX.X
Per-Protocol	Visit 1 /Day 1 (Baseline)	Actual Value	Min, Max	XX, XX	XX, XX	XX, XX
			N	XX	XX	XX
			Mean \pm SD	XX.X \pm XX.X	XX.X \pm XX.X	XX.X \pm XX.X
		Actual Value	Median	XX.X	XX.X	XX.X
			Min, Max	XX, XX	XX, XX	XX, XX
	Visit 5 /Day 8	Actual Value	N	XX	XX	XX
			Mean \pm SD	XX.X \pm XX.X	XX.X \pm XX.X	XX.X \pm XX.X
			Median	XX.X	XX.X	XX.X
		Change from Baseline	Min, Max	XX, XX	XX, XX	XX, XX
			Mean \pm SD	XX.X \pm XX.X	XX.X \pm XX.X	XX.X \pm XX.X
			Median	XX.X	XX.X	XX.X
			Min, Max	XX, XX	XX, XX	XX, XX

Note: Missing data will be replaced for the efficacy endpoint in the ITT analyses using the Last observation carried forward (LOCF) method.

Source: Listing 16.2.6.1

O:\Studies\EmitBio\EB-P12-01\Biometrics\Programs\Tables\xxx.sas ran on Month Day, Year at hh:mm on data from Month Day, Year.

Table 14.2.5.1 – Time to Alleviation of COVID-19 Symptoms

Population	Statistics	4 Days RD-X19	7 Days RD-X19	Sham
Intent-to-Treat	N	XX	XX	XX

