				Date (Study Day)	Time					
Treatment:										

Study Day is calculated relative to date of first treatment. Day 1 is the day of first treatment.

O:\Studies\ EmitBio\EB-P12-01\Biometrics\Programs\Listings\xxx.sas ran on Month Day, Year at hh:mm on data from Month Day, Year

Listing 16.2.6.4 – Derived Clearance of Viral Infection and Time-Weighted Average Change from Baseline in Log10-Transformed Viral Load via RT-qPCR

Subject	Cohort	Analysis	Clearance of Viral Infection (Study Day)				Change from Baseline in Log10-Transformed Viral Load (Study Day)			TWA Change from Day 1 to Day 8
			Visit 2 /Day 2	Visit 3 /Day 3	Visit 4 /Day 5	Visit 5 /Day 8	Visit 3 /Day 3	Visit 4 /Day 5	Visit 5 /Day 8	
Treatment:										
	ITT		No (2)	No (3)	No (5)	No (9)	xx.x (3)	xx.x (5)	xx.x (9)	xx.x
	PP		No (2)	No (3)		No (9)	xx.x (3)		xx.x (9)	xx.x

Abbreviation: ITT = Intent-to-Treat, PP = Per-Protocol, TWA = Time-Weighted Average, LOCF = Last observation carried forward
Study Day is calculated relative to date of first treatment. Day 1 is the day of first treatment.

For the ITT analysis, missing viral load will be imputed using the LOCF method.

Note 1: Clearance of viral infection is defined, based on viral load via RT-qPCR, as achievement of: [1] RP Ct ≥ 0 , AND [2] Average N1 Ct ≥ 32 or Average N1 Ct = “Undetermined”.

Note 2: TWA Change from Day 1 to Day 8 is calculated using the trapezoidal rule.

O:\Studies\ EmitBio\EB-P12-01\Biometrics\Programs\Listings\xxx.sas ran on Month Day, Year at hh:mm on data from Month Day, Year

Listing 16.2.7 - Adverse Events

Subject	Cohort	AE No.	System Organ Class / Preferred Term / Event Name	Occurred prior to first dose?	Start Date (Study Day)	Stop Date (Study Day)	Serious AE?	Intensity	Causality to Study Device	Action Taken	Outcome
Treatment:											

Note: Adverse events coded in MedDRA, version xx.x

Study Day is calculated relative to date of first treatment. Day 1 is the day of first treatment while Day -1 is the day prior to first treatment.

O:\Studies\EmitBio\EB-P12-01\Biometrics\Programs\Listings\xxx.sas ran on Month Day, Year at hh:mm on data from Month Day, Year

Listing 16.2.8.1 – Out-of-Range Results of Clinical Laboratory Tests

Subject	Cohort	Visit	Lab Panel	Test Name	Result	Flag	Out of Range: NCS or CS
---------	--------	-------	-----------	-----------	--------	------	-------------------------

Treatment:

Abbreviation: CS = clinically significant, NCS = not clinically significant

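### ITT LOCF fills a missing Day 3 or Day 5 viral load even when a later sample exists, and Table 14.2.4 extends LOCF to the severity score, outside the one exception in protocol 10.4

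*Combined protocol and SAP*

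**What the plan says.** **Viral load.** SAP 5.2.1 gives the ITT rule: "Missing data will be replaced for the efficacy endpoint in the ITT analyses using the Last observation carried forward (LOCF) method". Note 1 to Table 14.2.1.1 (the primary table) and the note to Table 14.2.2.1 repeat it, and the footnote to Listing 16.2.6.4 reads "For the ITT analysis, missing viral load will be imputed using the LOCF method". None of these restricts LOCF to dropout or to visits after the last sample. Protocol 10.4 has the same rule for viral load: "In general, missing data will not be imputed with the exception that for the ITT analysis, missing viral load results will be imputed" by LOCF.

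SAP 5.5.1 derives the TWA by the trapezoidal rule, where t "is the actual study day at the specified timepoint". Samples are scheduled at baseline and Days 3, 5 and 8. SAP 5.5 says "All virology data will be included in the efficacy analysis except the samples with" an inconclusive quantitation or an undetermined RNase P control, so an attended visit can still lack a usable value. The per-protocol (PP) version of the primary table is produced "with Note 1 removed", that is, without LOCF.

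**Severity score.** Table 14.2.4 carries the footnote "Note: Missing data will be replaced for the efficacy endpoint in the ITT analyses using the Last observation carried forward (LOCF) method". The SAP schedule (7.1) has the visit score only on Day 1 and Day 8/ET. SAP 5.1 adds that for early discontinuations "all efficacy assessments captured at the ET visit will be assigned to the nearest protocol scheduled time point".

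**The concern.** For an intermittent gap, LOCF assumes that viral load stayed flat up to the missing visit, when a later sample from the same subject may show that it fell. A missing Day 3 value is replaced by the pre-treatment baseline, a change of zero, if baseline counts as the last observation. Such gaps do not need dropout. They can come from unusable samples, or from a sample taken on Day 4, which SAP 5.1 maps to the Day 5 visit because the Day 3 window is Study Day 3 only.

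The imputation is not needed, because a trapezoid on actual days accepts unequal intervals. It also leaves the derivation open: SAP 5.5.1 asks for the actual day, a missed visit has none, and the SAP does not say which day to use. Two programmers could follow the SAP and get different primary values. Table 14.2.1.1 is also an interim output, where the target is only 10 sham subjects.

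For the severity score, a subject with no post-baseline score has only baseline available to carry forward. The table could then mix observed changes with imputed zeros that the protocol does not provide for.

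**Working it through.** The documents give no figure on this point, and no missingness rate or rate of viral decline. The weights and factors below are exact; the declines and gap counts are assumptions.

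**1. Weights on Days 1/3/5/8.** With Y the change from baseline (Y1 = 0) and a span of 7 days, the SAP 5.5.1 weights are 2/14, 4/14, 5/14 and 3/14.

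**2. Day 5 missing, Day 8 observed.**
- LOCF: (9/14)·Y3 + (3/14)·Y8
- Observed-sample trapezoid: (7/14)·Y3 + (5/14)·Y8
- Difference: (2/14)(Y3 − Y8) = (Y3 − Y8)/7

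**3. Day 3 missing, baseline carried.**
- LOCF: (5/14)·Y5 + (3/14)·Y8
- Observed-sample trapezoid: (7/14)·Y5 + (3/14)·Y8
- Difference: −(2/14)·Y5 = (Y1 − Y5)/7

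In both cases the shift toward zero is 1/7 of the observed fall between the neighbouring samples, about 0.14 log10 per 1 log10.

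**4. Other visit days (windows in SAP 5.1).** For a gap at t2 after t1, the factor is (t2 − t1)/[2(tb − ta)].
- Imputed value at its target day, Day 8 visit on Days 7–9: 2/(2×8) to 2/(2×6) = 0.125 to 0.167, for a Day 3 or a Day 5 gap.
- Attended Day 5 visit on Days 4–6 with an unusable sample: (4−3)/(2×8) = 0.0625 to (6−3)/(2×6) = 0.25. This wider range does not apply to a missed visit.

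**5. Assumed courses, TWA on Days 1/3/5/8.**

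| Course | Missing | Complete | LOCF | Observed samples |
|---|---|---|---|---|
| Linear, 0.5 log10/day | Day 3 | −1.750 | −1.464 | −1.750 |
| Linear, 0.5 log10/day | Day 5 | −1.750 | −1.393 | −1.750 |
| Linear, 0.5 log10/day | Both | −1.750 | −0.750 | −1.750 |
| Rise then fall (0, +0.5, −0.5, −2) | Day 3 | −0.464 | −0.607 | −0.679 |
| Rise then fall | Day 5 | −0.464 | −0.107 | −0.464 |
| Rise then fall | Both | −0.464 | −0.429 | −1.000 |

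The observed-sample trapezoid is exact for a linear decline. For the rise-then-fall course LOCF is closer to the complete-data value when Day 3, or both visits, are missing.

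**6. Arm difference, Day 5 gaps.** The fall from Day 3 to Day 8 at b log10/day is 5b. The shift is (p_device × 5b_device − p_sham × 5b_sham)/7.
- 10% in each arm, equal declines: 0.
- 10% in each arm, 0.6 vs 0.4 log10/day: 0.1 × (3.0 − 2.0)/7 = 0.014. The TWA difference is 0.2 × 3.5 = 0.70, so this is 2%.
- 3 of 20 device vs 0 of 20 pooled sham, b = 0.1 / 0.3 / 0.7: 0.15 × 5b/7 = 0.01 / 0.03 / 0.08, understating the difference.
- Interim, 0 of 20 device vs 2 of 10 sham, same b: 0.2 × 5b/7 = 0.01 / 0.04 / 0.10, overstating it.

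**7. Severity score.** If one of 20 subjects is given a change of zero and the other 19 average m, the mean is 19m/20 = 0.95m, a 5% shrinkage. At an assumed m of −0.5 to −1.0 on the 0–3 scale, that is 0.025 to 0.05 points.

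**The case against.** LOCF for ITT viral load is prespecified in the protocol, so changing it creates a departure where none exists now. The trial is hypothesis-generating, its p-values are descriptive (SAP 5.1), and balanced gaps barely move the arm difference. The PP table already omits LOCF and covers Day 5 gaps. The shifts above are measured against a straight line and not against the truth, and the rise-then-fall course shows that the straight line can do worse. The Listing 16.2.6.4 shell, which fills Day 5 in the ITT row and leaves it blank in the PP row although both have a Day 9 value, is a mock row. It also shows a Day 2 clearance result, although no Day 2 specimen is scheduled.

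Most of this stands and lowers the importance. The shell is illustrative, but the unrestricted wording of SAP 5.2.1 leads to the same result without it. PP is only a partial check: the absence of a Day 3 visit is a listed major deviation (SAP 4), so a subject who missed it may be analysed only with LOCF.

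On severity, protocol 10.4 speaks in general terms and leaves details to the SAP, and LOCF could bring an early-termination score from Days 4–6 into the Day 8 row. The first does not create a second exception beside viral load; the second can be met by placing the observed ET score in that row.

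A reader might infer that LOCF ignores the later sample. It does not: that sample keeps a reduced weight. A reader might also infer that the primary comparison is biased against or in favour of the device. The documents give no missingness or decline rate to support either.

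**Conclusion.** The point holds as a method weakness of minor to moderate importance. For an intermittent Day 3 or Day 5 gap, the ITT rule moves the subject's TWA toward zero by 1/7 of the fall between neighbouring samples, relative to a trapezoid that the SAP formula already permits. The factor is 0.125 to 0.167 when the imputed value sits at its target day. For a steadily declining course LOCF is the worse value; for a rise-then-fall course it need not be. The effect on the arm difference is small if gaps are few and balanced, and of either sign if not; every group-level figure rests on assumed declines and gap counts. There is no protocol–SAP conflict on viral load.

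The severity table is different: its LOCF note goes beyond the only exception that protocol 10.4 names. Imputed zeros arise only if baseline may be carried forward, which the SAP neither states nor excludes.

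**What to change.** In SAP 5.2.1 and 5.5.1, state:

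> In ITT and PP, TWA is computed from analysis-qualified samples at their actual study days; a visit without such a sample is omitted when a later sample exists. In ITT, if no Day 8 sample exists, the last observed change is carried to Day 8 (the actual study day if the visit was attended, otherwise t = 8). LOCF at every missing visit, at the actual study day if attended and otherwise at the target day, is a sensitivity analysis.

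Also state the PP rule for a missing Day 8 sample and the rule for a subject with no post-baseline sample. Align the notes to Tables 14.2.1.1 and 14.2.2.1 and Listing 16.2.6.4, so that visit means and the TWA treat the same gap alike, and record the departure from protocol 10.4.

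In Table 14.2.4, replace the LOCF note with: *Observed scores only; baseline is not carried forward.* Label the second row Visit 5 /Day 8/ET, as Tables 14.3.4 and 14.3.5 do, and state that an observed ET score goes there. Under SAP 5.1 an ET on Days 4–6 would otherwise map to Day 5, which has no row in this table.

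The cost is SAP wording, a few derivation lines, one sensitivity table and one relabelled row; no new data. The downsides are a straight-line assumption across the gap, slightly fewer subjects in the severity table, and some earlier ET scores mixed with Day 8 scores. LOCF for a missing Day 8 viral load remains, and the 95%-reduction responder table is not addressed.

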5.2.2 Missing or Incomplete Dates for Adverse Events and Concomitant Medications

Adverse Events

Handling of partial dates is only considered for the start date. An adverse event with a partial start date is considered treatment emergent if:

- only the day is missing and the start month/year is the same or after the month/year of the first treatment
- the day and month are missing and the start year is the same or greater than the year of the first treatment date
- the start date is completely missing

Concomitant Medications

Handling of partial dates is only considered for the stop date. A medication with a partial stop date is considered concomitant if:

- only the day is missing and the stop month/year is the same or after the month/year of the first treatment
- the day and month are missing and the stop year is the same or greater than the year of the first treatment date
- the stop date is completely missing or the medication is ongoing.

5.3 Demographics and Baseline Characteristics

Demographics and baseline characteristics will be summarized descriptively for the Safety population.

5.4 Subject Accountability

A summary of subject disposition will be provided for all subjects descriptively, including reason for discontinuation and analysis populations.

5.5 Efficacy Variables and Analyses

All efficacy analyses will be performed for both the ITT and PP populations with results in ITT as primary and PP as supportive.

Viral load (log base 10 copies/mL) and cycle threshold (Ct) data that are continuous in nature but may be reported as “undetermined” or “inconclusive” or “<LOQ”. All virology data will be included in the efficacy analysis except the samples with “Inconclusive” viral load quantitation and the samples with an “Undetermined” RNase P (RP) internal control Ct value.

For analysis-qualified samples, results of “undetermined” and “<LOQ” will be handled as follows for data summary purpose:

- For viral load reported as “Undetermined”, value 1 will be used to calculate descriptive statistics. This will support the need for logarithm transformation.
- For viral load reported as “<LOQ”, value 5×10^1 will be used to calculate descriptive statistics.

In conjunction with above handling of the viral data scenarios, for purposes of this protocol, clearance of viral infection is defined as achievement of: [1] RP Ct ≥ 0 , AND [2] Average N1 Ct ≥ 32 or Average N1 Ct = “Undetermined”.

